7.8.3.8. Accidental Exposure

Based on the data in the accidental exposure questionnaire, the following accidental exposure endpoints will be summarized for each treatment group:

- Number and percent of subjects with any accidental exposures
- Number and percent of subjects with any accidental exposures requiring treatment
- Number and percent of subjects with any accidental exposures requiring epinephrine use
- Number and percent of subjects with any accidental exposures requiring hospitalization
- Number and percent of subjects with AEs due to accidental exposures

In addition, the accidental exposures will be summarized by period for each treatment group.

7.8.3.9. Maximum Severity of Allergy Symptoms Assessed During DBPCFCs

The severity of symptoms will be assessed at Screening DBPCFCs and Exit DBPCFCs. Grading of symptoms will be done using the grading definition in the Oral Food Challenge (OFC) Symptom Score Sheets. Symptom severity will be determined at 6 levels: 0-None, 1-Mild, 2-Moderate, 3-Severe, 4-Life Threatening, and 5-Death. Subjects who experience no symptoms will be assigned a severity of 0-None. Symptom severity data will be collected at each challenge dose of food source during the Screening DBPCFCs (1, 3, 10, 30, 100, 300, 600, or 1000 mg) and the Exit DBPCFCs (1, 3, 10, 30, 100, 300, 600, 1000, 2000, or 4000 mg).

The maximum severity of symptoms observed in the DBPCFC at any dose ((screening: 1000 mg or lower) and (Exit Food Challenge/Week 40: 4000 mg or lower)) will be used for each subject in the analysis of this endpoint.

The number and percent of subjects by maximum severity at the Screening and Exit DBPCFCs for each qualifying food at any dose will be provided by treatment group. The summary will be repeated for non-qualifying reactive food at any dose level.

Severity of symptoms data will be listed.

The maximum severity of allergy symptoms at any dose and at each dose of the Screening and Exit DBPCFCs for each qualifying food will be graphically displayed, respectively.

7.8.3.10. Maintenance Dose for Study Drug

The maintenance dose (mg/day) will be summarized by treatment group using descriptive statistics (median, min, max, and Q1:Q3). The number and percentage of subjects whose maintenance dose is 50, 100, 200, 400, 700, 1000, 1500, 3000, or 4500 mg/day will be provided as well. If a subject exits the study prior to achieving a dose of at least 50 mg, then the maintenance dose will be set to missing.

The time to achieving the maintenance dose level is defined as [(first dose date of maintenance dose) – (first dose date of study drug) + 1]. The maintenance dose for these individuals can be determined once the subject has started the exit challenge procedure (i.e. maintenance is the week 38 dose level), reached the target dose for their randomized treatment group or discontinued the study. The time to achieving first maintenance dose will be presented for the treatment period using Kaplan-Meier (KM) method. Subjects who do not reach a maintenance dose will be censored at the date of their last study drug dose. KM curves will be plotted separately for the pooled placebo, low-dose and high-dose groups. A similar method will be repeated for time to achieving target dose level (1500 mg/day for low-dose and 4500 mg/day for high-dose) as maintenance dose.

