The updosing regimen is shown in Table 3 and should be followed as described in Section 6.5.1.

Table 3: Study Drug Updosing Regimen

Total Protein ADP101 per Day (mg)	Low-Dose Regimen	High-Dose Regimen	Increase (%)	Minimum Approximate Total Amount of Qualifying Reactive Food Source (for Subjects Allergic to 1 Food in ADP101) (mg)	Maximum Approximate Total Amount of Qualifying Reactive Food Source (for Subjects Allergic to 5 foods in ADP101) (mg)
5	X	X	_	0.3	1.6
20	X	X	303	1.3	6.6
50	X	X	150	3.3	16.6
100	X	X	100	6.6	33.3
200	X	X	100	13.3	66.6
400	X	X	100	26.6	133.3
700	X	X	75	46.6	233.3
1000	X	X	43	66.6	333.3
1500	X	X	50	100	500
3000	NA	X	100	200	1000
4500	NA	X	50	300	1500

Abbreviations: NA = not applicable.

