7.8.3.11. Target Attainment

100% target attainment occurs when a subject attains the randomized target dose of 1500 mg/day for low-dose regimen or 4500 mg/day for high-dose regimen. A subject's target attainment at MD is expressed as a percentage, calculated as [(maintenance Dose) / (target dose level) × 100].

The number and percent of subjects who attained randomized target levels of 1500 mg/day (low-dose regimen) or 4500 mg/day (high dose regimen) by visit will be provided. The target attainment at MD will be summarized using continuous and categorical (e.g., 100%, $\geq 90\%$ - < 100%, $\geq 80\%$ - < 90%, < 80%) descriptive statistics. The proportion of subjects with 100% target attainment versus visit along with CI will be plotted. A swimmer plot showing individual exposure to study drug (in weeks) over time by treatment group and dose level, will also be provided.

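### Subjects who never reach 50 mg drop out of the maintenance-dose summary and of attainment at the maintenance dose, and two of the four example attainment bands cannot occur

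*SAP*

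**What the plan says.** **Missing rule.** Under SAP 7.8.3.10, if someone leaves the study before "achieving a dose of at least 50 mg, then the maintenance dose will be set to missing". The maintenance dose is described by median, minimum, maximum and quartiles; no mean is listed. Counts are also given for subjects whose "maintenance dose is 50, 100, 200, 400, 700, 1000, 1500, 3000, or 4500 mg/day".

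**Attainment.** SAP 7.8.3.11 defines full attainment as the case where a subject "attains the randomized target dose of 1500 mg/day for low-dose regimen or 4500 mg/day for high-dose regimen". Attainment at MD (the maintenance dose) is the maintenance dose divided by the target, times 100. "The target attainment at MD will be summarized using continuous and categorical" statistics, with four bands offered as examples: 100%, 90 to <100%, 80 to <90%, and <80%. Under SAP 6.1 the default continuous summary includes a mean, and the default denominator for percentages is N per treatment group unless the shell says otherwise.

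**Definition.** SAP 6.2.1 defines the maintenance dose as the last dose before the Exit food challenge or End of Treatment that was tolerated for at least 2 weeks. It sets no 50-mg floor.

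**Who stays in the study.** Protocol 6.5.1 and its Table 5 have subjects who cannot tolerate 5, 20 or 50 mg stop study drug but remain in the study.

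**The concern.** A subject who tried and could not reach 50 mg has a known, poor tolerability result. Setting the dose to missing takes that result out of the summaries meant to show how far each regimen can be taken, and the more subjects it happens to, the better the rest look. The SAP places poor results at the bottom elsewhere: anyone who does not meet the response definition is a non-responder (7.8.1), and a subject who tolerates no challenge dose is given 1 mg for the fold-increase calculation (7.8.3.2).

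The rule is also incomplete. It speaks of leaving the study, while the protocol keeps those who fail 50 mg in the study off drug. For them, 6.2.1 could yield 5 or 20 mg, but the dose table has no row below 50 mg.

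The example bands add little if no dose can fall in two of them. Protocol 4.2 gives assessment of the low- and high-dose regimens as part of the design rationale, and these outputs bear on that.

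**Working it through.** The documents give no figure for this output to reproduce. The check has two parts.

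**1. Bands against the ladder.** Inputs: the dose levels in Protocol 6.1 ("Table 3: Study Drug Updosing Regimen") and the targets of 1500 and 4500 mg/day. Formula: level / target × 100.

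| Level (mg) | Low, /1500 | High, /4500 |
|---|---|---|
| 5 | 0.3% | 0.1% |
| 20 | 1.3% | 0.4% |
| 50 | 3.3% | 1.1% |
| 100 | 6.7% | 2.2% |
| 200 | 13.3% | 4.4% |
| 400 | 26.7% | 8.9% |
| 700 | 46.7% | 15.6% |
| 1000 | 66.7% | 22.2% |
| 1500 | 100% | 33.3% |
| 3000 | not used | 66.7% |
| 4500 | not used | 100% |

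The highest value below target is 1000/1500 = 3000/4500 = 66.7%. Nothing lies from 80% to just under 100%, so two bands are always empty. The other two reduce to target reached or not reached.

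**2. Effect of the missing rule.** The documents give no count of subjects who never reach 50 mg, so this part is an illustration under assumptions. Take the 20 pediatric subjects per active arm in SAP Table 1 and the high-dose regimen. Assume 10 at 4500 mg, k who never reach 50 mg, and the other 10 − k split between 3000 and 1500 mg (an odd one goes to 1500). Under the planned 20% dropout, 0.20 × 20 = 4 leave per arm, so k = 4 means that every planned dropout leaves before 50 mg.

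| k | At 3000 / 1500 | Sum of attainment (%) | Mean, k omitted | Mean, k as 0% |
|---|---|---|---|---|
| 1 | 4 / 5 | 1433.3 | /19 = 75.4% | /20 = 71.7% |
| 2 | 4 / 4 | 1400.0 | /18 = 77.8% | /20 = 70.0% |
| 3 | 3 / 4 | 1333.3 | /17 = 78.4% | /20 = 66.7% |
| 4 | 3 / 3 | 1300.0 | /16 = 81.25% | /20 = 65.0% |

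The sum is 10 × 100 + (number at 3000) × 66.67 + (number at 1500) × 33.33. As k rises, the planned mean rises while the full-arm mean falls.

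- Median dose: 4500 mg with the k omitted; (4500 + 3000)/2 = 3750 mg with all 20.
- Minimum: 1500 mg with the k omitted; 0 with all 20.
- Percent at 100%: 10/20 = 50% on denominator N for every k. It would rise to 10/19 = 52.6% through 10/16 = 62.5% only if the shell used non-missing subjects.

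**The case against.** The strongest reply is that a missing value is sometimes right. The 50-mg step comes after 2 weeks at 5 mg and 2 weeks at 20 mg. A subject who withdraws or is lost in those first 4 weeks has shown no intolerance of 50 mg, and a blanket 0 mg would record a failure that nobody observed. This stands, and it is why the fix splits these subjects by reason and keeps the planned version alongside.

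Early failures are also visible elsewhere: the flag for leaving without a maintenance dose (SAP 6.4.3), reasons for stopping treatment (7.1), exposure by dose level and unsuccessful increases (7.7), adverse events leading to discontinuation (7.9.1), and the Kaplan-Meier analysis, which keeps these subjects, though censored. That limits the harm but does not correct the two summaries at issue.

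The bands are only examples, the shells are in a separate document, and 7.8.3.10 already counts subjects at each level from 50 mg up. A reader might therefore infer too much from the empty bands: the planned output as a whole does distinguish 3000 mg from 50 mg, and only the example bands do not.

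**Conclusion.** The point holds for the maintenance-dose median, quartiles and minimum, for continuous attainment at MD, and for the dose rows and bands, in which these subjects do not appear. That two example bands are empty is exact arithmetic. The size of the first effect rests on the assumed dose split and on k: a gap in mean attainment from 3.8 points (1433.3/19 − 1433.3/20) to 16.25 points (81.25 − 65.0) for k = 1 to 4.

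Broader readings are tempting, but the documents do not support them:

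- **Average dose is inflated.** No mean maintenance dose is listed, and the average daily dose in SAP 7.7 does not use this rule.
- **All target attainment excludes poor tolerators.** Attainment by visit and the swimmer plot do not use the maintenance dose, and the percent at 100% is not inflated on the default denominator N.
- **Efficacy is affected.** Primary responder status does not depend on the maintenance dose.

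The output is exploratory and descriptive. Severity: minor.

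**What to change.** 1. **SAP 7.8.3.10 and 6.2.1.** Add a row for no maintenance dose / <50 mg, on denominator N, for all treated subjects who never reach 50 mg, whether they leave the study or stay in it off drug. Split it into failed updosing and left before 50 mg was attempted. Align 6.2.1 so that a tolerated 5 or 20 mg is handled in one stated way.
2. **Continuous summaries.** Present the maintenance-dose quantiles and attainment at MD with these subjects ranked lowest (0% attainment), beside the version restricted to subjects with a maintenance dose.
3. **SAP 7.8.3.11.** Replace the example bands with ones the ladder can fill in both regimens, for example 100%; 66.7% (one level below target); 25 to <66.7%; >0 to <25%; none.

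The cost is a few lines of SAP text and the matching table shells. No new data are needed: the flag in SAP 6.4.3, the in-clinic dosing records and the recorded reasons for stopping treatment already hold what the row and its split require.

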2. Non-reactive Food, defined as foods that either a) do not meet clinical history and/or biomarker threshold criteria (SPT ≤ 3 mm above negative control) to undergo a Screening DBPCFC, or b) meet criteria to undergo a Screening DBPCFC and are tolerated through the 1000-mg dose level at the Screening DBPCFC

Subjects who are found to meet the categorization of Reactive Food that include qualifying food sources (to at least 1 and no more than 5 foods) will satisfy screening criteria to be randomized as long as they meet all other eligibility criteria.

Pre-Maintenance of the Treatment Period: At baseline (of the treatment period), eligible subjects will be randomized in a 2:2:1:1 ratio to 1 of 4 arms, with 2 arms in each dosing regimen

(low or high), to receive daily oral doses of study drug (either ADP101 or matching placebo) in a blinded fashion as shown in [Table 1](#). Subjects will be assigned to the low- or high-dose regimen but will be blinded to whether their regimen is the active or placebo study drug. Randomization will be stratified by age group (≥ 4 to < 18 years of age, and ≥ 18 to ≤ 55 years of age). Baseline treatment will consist of oral administration of a single dose of study drug at 5 mg (equivalent to 0.33 mg/food source) under direct medical supervision at the study site, and, if tolerated, will continue at 5 mg/day at home for 2 weeks. Subjects who are unable to tolerate up to 3 attempts to administer study drug at dose levels at or below 50 mg during the updosing portion of the treatment period will discontinue study drug and continue with study assessments. If a subject is unable to tolerate 5 mg after 3 tries, this will trigger randomization of another subject.

Table 1 Treatment Groups

| Treatment Group | Treatment | Regimen | Target Dose Level | Estimated Number of Subjects | Estimated Number of Subjects per Age Group Category (years) | |
|-----------------|-----------|-----------|---|------------------------------|---|------------------------|
| | | | | | ≥ 4 to < 18 | ≥ 18 to ≤ 55 |
| 1 | ADP101 | Low-dose | 1500 mg/day (100 mg per food source) | 24 | 20 | Approximately 4 |
| 2 | ADP101 | High-dose | 4500 mg/day (300 mg per food source) | 24 | 20 | Approximately 4 |
| 3 | Placebo | Low-dose | (Content volume-matched) | 12 | 10 | Approximately 2 |
| 4 | Placebo | High-dose | (Content volume-matched) | 12 | 10 | Approximately 2 |

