Subjects who tolerate at least 50 mg/day will continue in the updosing portion of the study, and will return to the clinic every 2 weeks for updosing under direct medical supervision until the randomized target dose of 1500 mg/day (100 mg per food source; low-dose regimen) or 4500 mg/day (300 mg per food source; high-dose regimen) is achieved ([Figure 1](#)). If a subject fails 3 updosing attempts to any dose level above 50 mg/day, the site should contact the Study Medical Monitor for further guidance regarding additional updosing. Subjects who are unable to reach the randomized target dose will continue on the highest dose level they are able to reach, as long as the dose of study drug is at least 50 mg. Subjects may updose through Week 38, at which point the Week 38 dose will be maintained through the end of the study. Therefore, the duration of pre-maintenance (during the treatment period) is anticipated to be of variable length depending on how quickly subjects are able to reach their randomized target dose or maintenance dose.

Maintenance of the Treatment Period: Once the randomized target dose (or maintenance dose) is achieved, it will be maintained until Week 40. The maintenance portion of the treatment period may range from 2 to 22 weeks. Once a subject enters maintenance (e.g., no further updosing is planned), study visits will continue at every 2 weeks; however, on-site visits can be

spaced out to every 4 weeks and the other visits performed via tele-visit.. Vital signs and physical examination can be skipped for these visits. The Weeks 12, 20, 24, and 38 visits must be performed on-site.

Exit Food Challenge/Week 40 Visit: At the Week 40 visit, all subjects will undergo an Exit DBPCFC for all Reactive Foods determined during Screening. The Week 40 visit will be done over multiple visits (for up to 6 weeks, or extended to up to 8 weeks if a subject requires > 6 food challenges) to allow for adequate separation of individual DBPCFC procedures. The Exit DBPCFCs ([Figure 4](#)) will be performed in accordance with Practical Allergy (PRACTALL) guidelines ([Sampson, 2012](#)) and will require progression in an unaltered sequence, without repeating any dose. The Exit DBPCFCs will assess the same levels as done at study entry, as well as evaluating higher levels of up to 4000 mg of protein of each reactive food source (see [Figure 4](#)).

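### The Kaplan-Meier curve for time to target dose censors subjects who stop study drug, so it can overstate attainment by a factor of up to 1.25 at the planned 20% dropout (SAP 7.8.3.10)

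*SAP*

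**What the plan says.** SAP 7.8.3.10 sets the estimator: "The time to achieving first maintenance dose will be presented for the treatment period using Kaplan-Meier (KM) method". The censoring rule follows: "Subjects who do not reach a maintenance dose will be censored at the date of their last study drug dose". On grouping, "KM curves will be plotted separately for the pooled placebo, low-dose and high-dose groups". For the target dose (1500 mg/day low, 4500 mg/day high, counted when it is the maintenance dose) the text is brief: "A similar method will be repeated for time to achieving target dose level". No separate censoring rule is given for that second curve, and discontinuation is nowhere named as a competing event.

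Two other statements in the same section limit who is censored in the maintenance-dose curve. A maintenance dose can be fixed once the subject has started the exit challenge procedure, or has "reached the target dose for their randomized treatment group or discontinued the study". It is set to missing "If a subject exits the study prior to achieving a dose of at least 50 mg".

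On what stopping means, SAP 3.1 says that subjects who fail up to three attempts at or below 50 mg "will discontinue study drug and continue with study assessments"; Protocol Table 5 agrees. SAP 3.1 also fixes the last time at which the event can occur: "Subjects may updose through Week 38, at which point the Week 38 dose will be maintained through the end of the study".

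**The concern.** Kaplan-Meier censoring assumes that a censored subject would go on to have the event at the same rate as those still under observation. That fails here. Someone who has permanently stopped study drug will not reach a higher dose, and the documents make some of these stops mandatory because updosing failed, which is the process the curve is meant to describe. The estimator removes these subjects from the risk set and spreads their share over those who remain.

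At stake is the reading of a tolerability result. A curve that levels off at 75% will be read as three quarters of the arm reaching target. If the crude count in SAP 7.8.3.11 says 60%, one report carries two answers to nearly the same question without explanation. The approach also differs from the handling of the primary endpoint, where Protocol 9.4.3 counts subjects who stop before the Exit DBPCFC as failures.

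**Working it through.** **Inputs**
- Pediatric subjects per active arm: 20 (SAP Table 1).
- Planned pediatric dropout: 20% (SAP 3.2). The plan gives no figure for the Kaplan-Meier analysis itself, but its dropout arithmetic reproduces: 48/(1 − 0.20) = 60 randomized. Per active arm, 0.20 × 20 = 4.
- Dose levels: nine in the low regimen and eleven in the high regimen (Protocol Table 3), with one step every 2 weeks.
- Attainment counts and dropout timing are not in the documents, so they are varied below. All four dropouts are taken to stop study drug before reaching target.

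**Earliest possible target date.** Low: (9 − 1) × 2 = Week 16. High: (11 − 1) × 2 = Week 20. The longest maintenance portion given in SAP 3.1, 22 weeks, would imply 40 − 22 = Week 18 as the earliest. A later date only leaves more room for stops to fall before it.

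**Upper bound.** Suppose a fraction d of n subjects stop before anyone can reach target, and k later reach it. The risk set at the first event is n(1 − d), so

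1 − KM = k / [n(1 − d)], cumulative incidence = k/n, ratio = 1/(1 − d).

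With n = 20, d = 0.20 and k = 12 (say 8 at one visit and 4 at a later one): KM = (1 − 8/16)(1 − 4/8) = 0.25, so 1 − KM = 75%. Cumulative incidence is 12/20 = 60%. The ratio is 1.25.

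**Dropouts spread over Weeks 2 to 37.** Four evenly spaced stops fall at about Weeks 6.4, 15.1, 23.9 and 32.6. For the low arm with 8 attainers, one per visit from Week 16 to Week 30, 18 are at risk at Week 16. Four events take this to 14, one stop to 13, and four more events to 9. So KM = (14/18)(9/13) = 0.538 and 1 − KM = 46.2%, against 8/20 = 40%. The same calculation for the other cases gives:

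| Attainers of 20 | Cumulative incidence | 1 − KM, all 4 stop before earliest target | 1 − KM, spread, low | 1 − KM, spread, high |
|---|---|---|---|---|
| 8 | 40% | 50% (×1.25) | 46.2% (×1.15) | 47.3% (×1.18) |
| 12 | 60% | 75% (×1.25) | 72.6% (×1.21) | 72.6% (×1.21) |
| 16 | 80% | 100% (×1.25) | 100% (×1.25) | 100% (×1.25) |

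**Other numbers of stops before the earliest target date.** One of 20: 1/0.95 = 1.05. Two: 1/0.90 = 1.11. Six: 1/0.70 = 1.43.

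**Completers who stay below target.** They are censored after the last possible event and cause no bias. If 12 of 20 reach target and 8 plateau without stopping, both methods give 60%.

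**Maintenance-dose curve.** Only subjects who stop without a maintenance dose are censored. If 2 of 20 never tolerate 50 mg and the other 18 all get a maintenance dose, 1 − KM is 100% against 18/20 = 90%. With 1 or 4 such subjects, it is 100% against 95% or 80%.

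**The case against.** The strongest reply is that little depends on these curves and that the uninflated figure is already planned. Maintenance dose is an exploratory endpoint added in SAP 4.5, with no test attached. SAP 7.8.3.11 gives the number and percent reaching target by visit, a plot of the proportion with its confidence interval, and a swimmer plot. SAP 6.1 makes the whole group the default denominator unless a table shell says otherwise. All of that stands, and it limits the importance of the point. It does not make the curve right, and it is why a visible contradiction could arise.

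It is also fair to say that the written censoring rule concerns the maintenance dose, and that the target curve inherits it only through the reference to a similar method. The bias in the target curve depends on that reading. If another rule is intended, the plan does not state it.

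Four stronger readings are tempting, and the documents do not support them:
- That every dropout is censored in the maintenance-dose curve. SAP 6.2.1 and 7.8.3.10 allow a subject who stops after tolerating at least 50 mg for two weeks to be assigned a maintenance dose and count as an event.
- That the overstatement falls mainly on the ADP101 arms. SAP 3.2 assumes a single 20% rate and gives no split by arm.
- That counting an early plateau at a low dose as an event is part of this error. It follows from the endpoint definition, not from the censoring, and the planned dose distribution already shows it.
- That 1.25 is the expected inflation. It is the ceiling at 20% dropout, and subjects who leave after reaching target are not censored at all.

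**Conclusion.** The point holds as a minor one. The direction is certain: with discontinuers censored, 1 − KM is never below the cumulative incidence, and it is above it whenever a stop comes before the last attainment. For the target curve the factor is at most 1.25 at the planned 20% dropout, and about 1.15 to 1.25 when four of 20 stops are spread over Weeks 2 to 37. For the maintenance-dose curve the bias has the same sign but is smaller, because fewer subjects are censored.

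These sizes rest on assumed attainment counts and dropout times, on treating the 20% as stops before target, on the target curve using the stated censoring rule, and on reading the missing-maintenance-dose rule, which is worded for leaving the study, as also covering subjects who stop drug but stay in follow-up. No primary, secondary or safety result is affected.

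A related point of presentation holds for placebo. The two placebo regimens have different targets and earliest attainment dates four weeks apart (Week 16 and Week 20), so one pooled time-to-target curve matches neither active arm's schedule.

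**What to change.** In SAP 7.8.3.10, replace the Kaplan-Meier display with a cumulative incidence curve (Aalen-Johansen) in which permanent discontinuation of study drug before the event is a competing event. Keeping discontinuers event-free and at risk through Week 40 would serve equally well. State the rule explicitly for the target curve instead of relying on the reference to a similar method. Show the placebo time-to-target curve separately for the low and high regimens.

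The cost is one option in the survival procedure and one additional placebo curve. No new data are needed, since treatment termination and the last dose date are already taken from the End of Treatment eCRF. The curves will look slightly less favourable, and discontinuations will no longer pull them away from the proportions in SAP 7.8.3.11.
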